6.1.2 Treatment of Outliers

Individual concentration-time points, if considered anomalous, may be excluded from the analysis at the discretion of the pharmacokineticist following a review of the available documentation. Any such exclusion will be discussed with the sponsor and clearly outlined in the study report.

Entire individual treatment profiles for a subject may be excluded following review of the available documentation and discussion with the sponsor. However, results of analysis with and without the excluded profiles may be presented in the study report. Any such exclusion will be clearly listed in the study report along with justification for exclusion.

Any anomalous concentration values observed at predose will be identified and discussed in the CSR. Pharmacokinetic parameters will be computed if the predose concentration value is not greater than 5% of C_{max} for a given subject. If the predose concentration value is greater than 5% of C_{max} concentration on Day 1, then the PK parameter data for the given subject will be listed but excluded from the PK summaries and statistical analysis. Subjects who experience emesis during the course of the study will be excluded from the PK summaries and statistical analysis if vomiting occurs at or before 2 times median T_{max} .

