3.1.4.4 Part D: SAD and MAD in Subjects with CG

Three dose levels are planned for the subjects with CG (Table 3-5). Subjects will be enrolled in 3 sequential cohorts of 6 subjects each for a total of 18 subjects. The initial dose level for Part D will be based on the results from Parts A (Cohorts A1 through A4) and Cohorts B1 and B2. Subjects will receive study drug (AT-007 or placebo) on Day 1 and remain at the CRU for at

least 48 hours after the first dose. Subjects will then have a 5-day washout period (Day 1 postdose through Day 6 predose). Then, subjects who tolerated the single dose will take the same study drug QD for 27 consecutive days (Day 6 through Day 32, inclusive) for the multiple dosing portion of Part D. For each individual subject, the Investigator and the Sponsor will decide whether the subject can start the multiple dosing portion of Part D. The Investigator must consult the Sponsor. Starting the multiple dosing portion requires explicit agreement from the Sponsor. In the 27-day multiple dosing portion, subjects will take most of their doses at home (fasting conditions recommended). Progression to and the dose level for the next cohort will be dependent upon safety data through Day 12 and at least single dose PK and galactitol results from the previous cohort as well as additional Part B (and possibly Part C) results.

 Table 3-5:
 SAD and MAD Dose Cohorts in Subjects with Classic Galactosemia (Part D)

| Cohort | Dose | |
|--------|---|--------------------|
| D1 | AT-007 oral capsule on Day 1, dose 5 mg/kg (SAD portion), followed by a 5-day-washout, and AT-007 oral capsule QD for 27 days (MAD portion), dose TBD mg/kg (n = 4) | placebo (n = 2) |
| D2 | AT-007 oral capsule on Day 1, dose 20 mg/kg (SAD portion), followed by a 5-day-washout, and AT-007 oral capsule QD for 27 days (MAD portion), dose TBD mg/kg (n = 4) | placebo (n = 2) |
| D3 | AT-007 oral capsule on Day 1, dose TBD mg/kg (SAD portion), followed by a 5-day-washout, and AT-007 oral capsule QD for 27 days (MAD portion), dose TBD mg/kg (n = 4) | placebo (n = 2) |

n = number of subjects; MAD = multiple ascending dose; QD = once daily; SAD = single ascending dose; TBD = to be determined

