Within each cohort of up to 16 subjects, subjects will be randomly assigned in a 3:1 to AT-007 and placebo. Subjects will receive study drug (AT-007 or placebo) on Day 1 and remain at the CRU for at least 24 hours after the first dose. Subjects will receive 1 daily dose of the same study drug (AT-007 or placebo) for a total of 90 consecutive days. In the extension, subjects will take most of their doses at home. Subjects will have 1 in-clinic stay associated with the first dose, a second in-clinic stay with the last dose, and out-patient visits at Months 1 and 2. Subjects will return for the EOE Visit at 28 days after the last dose.

Maximum duration of study participation (Screening through EOE Visit) for an individual subject will be approximately 158 days for a de novo subject and approximately 218 days for a subject who was screened for Part D, completed Part D, and completed Part D Extension without requiring a screening visit for the Part D Extension and without counting any washout period between Part D and Part D Extension.

Table 3-7: 90-Day Dose Cohort in Subjects with Classic Galactosemia (Part D Extension)

| Cohort | Dose | |
|--------|---|-------------|
| DE1 | AT-007 oral capsule on Day 1, dose 20 mg/kg (SAD portion), followed by AT-007 | placebo |
| | oral capsule QD for a total of 90 days, dose 20 mg/kg (n=up to 12) | (n=up to 4) |

n = number of subjects; MAD = multiple ascending dose; QD = once daily; SAD = single ascending dose. Note: There may be up to 1 additional cohort if the decision is made to test more than 1 dose level. Regardless of whether there is 1 or 2 cohorts, the maximum number of subjects is 16. However, the number of cohorts and total number of subjects may increase if doses above 40 mg/kg are tested in additional cohorts. The overall number of subjects per cohort may be increased to address any potential lost-to-follow-up among subjects treated with either placebo or AT-007.

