2, 4, 6, 8, and 12 hours (± 5 minutes for all time points) after the dose. Also, blood samples for plasma AT-007 PK will be collected at 24, 36, and 48 hours (± 5 minutes for all time points) after the Day 7 dose; these collections will be taken on Day 8 and Day 9. A lumbar puncture will be done after the Day 7 dose to collect CSF for analysis of AT-007. For Cohort C1, the timing (hours after the dose) of the lumbar puncture will be based on plasma AT-007 PK results from Cohorts B1 and B2. For Cohort C2, the timing of the lumbar puncture was based on PK results from Cohorts B1, B2, and B3. For Cohort C3, the timing of the lumbar puncture will be based on PK results from Cohorts B1, B2, B3, and B4. The intent is to perform the lumbar puncture at the time of maximum observed concentration (T_{max}) after the Day 7 dose.

In Part D, for the Day 1 dose, blood samples for plasma AT-007 PK will be collected predose (within 60 minutes before the dose) and at 0.5, 1, 1.5, 2, 4, 6, 8, 12, 24, 36, and 48 hours (± 5 minutes for all time points) after the dose. On Days 12 and 32, blood samples for plasma AT-007 PK will be collected predose (within 60 minutes before the dose) and at 0.5, 1, 1.5, 2, 4, 6, 8, and 12 hours (± 5 minutes for all time points) after the dose. On Day 13, a blood sample for plasma AT-007 PK will be collected predose (ie, at 24 hours ± 5 minutes after the Day 12 dose). On Day 33, blood samples for plasma AT-007 PK will be collected at 24 and 36 hours (± 5 minutes for both time points) after the Day 32 dose. On Day 34, a blood sample for plasma AT-007 PK will be collected at 48 hours (± 5 minutes) after the Day 32 dose.

For Cohort D3 only, urine for PK will be collected predose (spot collection within 60 minutes before the Day 1 dose) and in 4-hour intervals (0 to 4, > 4 to 8, > 8 to 12, > 12 to 16, > 16 to 20, and > 20 to 24) through the first 24 hours after the Day 1 dose followed by 12-hour intervals (> 24 to 36, > 36 to 48, > 48 to 60, and > 60 to 72) from 24 to 72 hours after the Day 1 dose. Allowable windows for urine collection container changes will be \pm 30 minutes through the first 24 hours and \pm 1 hour thereafter.

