7.5 Analysis Populations

Two analysis populations will be defined:

• Screened Population (SP): The screened population will consist of all subjects who are screened independent if they were eligible or not.

- Randomized Population: The randomized population will consist of all subjects who are randomized to any cohort.
- Safety Population: The safety population will consist of all subjects who are randomized and receive at least 1 dose of study drug. All analyses will be performed according to treatment received. This population will be used for all analyses of safety data and biomarker data.
- Pharmacokinetic Population: The PK population will consist of all subjects who receive at least 1 dose of AT-007 and have sufficient concentration-time data to estimate at least one of the planned PK parameters, as determined by the study Pharmacokineticist. This population will be used for all analyses of PK.

For Parts D and E, the safety and PK population may be defined separately for the SAD and MAD periods.

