7.10 Analysis of Pharmacokinetic Data

Plasma and urine PK parameters of AT-007 (including metabolites if determined) will be summarized by dose level and part using descriptive statistics. CSF concentration of AT-007 for cohort C1, C2 and C3 will be summarized by Cohort.

The PK Population will be used for all listings, concentration summaries, PK summaries and statistical analysis. The individual sampling and subject concentration-time for plasma and CSF concentrations will be listed and displayed graphically (plasma only) on linear and semi-log scales. The plasma and CSF drug concentrations will be summarized descriptively by nominal time point, Part and Cohort in tabular and graphical (plasma only) formats (linear and semi-log scales). The amount of AT-007 in urine will be listed by subject and summarized by nominal collection interval, Part and Cohort. Summary statistics will include: n, arithmetic mean, standard deviation (SD), coefficient of variation (CV%), median, minimum, maximum, and geometric mean (GM).

Pharmacokinetic parameters for AT-007 will be listed and summarized descriptively by Part, Cohort and Day, including n, arithmetic mean, SD, minimum, median, maximum, CV(%),GM, geometric SD, geometric CV%; geometric CV% calculated as the square root of the exponentiated SD of the natural log transformed data (SQRT(exp(sln^2)-1)), where appropriate. For t_{max} , only n, minimum, median, and maximum will be reported.

The dose proportionality of the primary PK parameters, AUC_{last} , AUC_{inf} and C_{max} after single dose (Part A, Part D and E, single dose portion) and AUC_{tau} , and C_{max} for single and multiple doses, over the administered dose range will be investigated using the following power model,

log(PK parameter) = a + b * log(dose), where a is the intercept and b is the slope.

Dose proportionality will be assessed for each part of the study separately. Furthermore, pooling of data across all parts at same dose level may be used to access overall dose proportionality for the entire range of the administered doses. However, pooling will be based on either the Day 1 dose or following multiple doses.

Each log-transformed PK parameter will be fit with a power model with a fixed effect term for log-transformed dose. For each PK parameter, the slope and associated 90% CI will be presented. A minimum of 3 values per dose cohort must be available for a given parameter to estimate dose proportionality with the power model.

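### The SAP's emesis rule excludes the whole subject from PK summaries and names no reference dose; applied literally in the 28- and 90-dose parts, it drops valid profiles

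*SAP*

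**What the plan says.** SAP 6.1.2 (Treatment of Outliers) contains the rule: "Subjects who experience emesis during the course of the study will be excluded from the PK summaries and statistical analysis". A condition follows: the vomiting must occur no later than two times median Tmax. The sentence does not say after which dose that time is counted, and it does not confine the exclusion to one profile, day or period.

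The same section has a separate, discretionary provision: "Entire individual treatment profiles for a subject may be excluded following review of the available documentation and discussion with the sponsor". It is not tied to emesis. SAP 7.5 adds that for Parts D and E "the safety and PK population may be defined separately for the SAD and MAD periods".

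On dosing, SAP 3.1.4.4 gives a single dose on Day 1 and then "study drug QD for 27 consecutive days (Day 6 through Day 32, inclusive"; SAP 3.1.4.5 gives Part E the same regimen. SAP 3.1.4.6 gives daily dosing in the Part D Extension "for a total of 90 consecutive days". On sampling in Part D, SAP 3.1.7 has a full profile after the Day 1 dose and then: "On Days 12 and 32, blood samples for plasma AT-007 PK will be collected predose", with serial post-dose samples on both days. Part E has the same schedule. The Extension has post-dose samples on Days 30, 60 and 90; its Day 1 sample is predose only.

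SAP 7.10 sets a floor for the dose-proportionality analysis: "A minimum of 3 values per dose cohort must be available for a given parameter to estimate dose proportionality with the power model".

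**The concern.** An exclusion by subject suits a single-dose study, where the subject and the profile are the same thing. In Parts D and E and the Extension they differ. Each subject contributes three profiles, weeks apart, and takes most doses on days with no PK sampling.

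Take a subject who vomits an hour after a home dose on Day 25. (In Parts D and E the clinic doses are Days 1, 6, 12, 13, 20 and 32, per Protocol Appendices D and E.) The Day 1 and Day 12 profiles are already complete and cannot have been altered, and Day 32 follows six further scheduled doses. Followed to the letter, the rule takes all three out of the summaries and the analysis. Vomiting after the Day 32 dose would likewise take out Days 1 and 12.

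At stake are the PK summaries and dose-proportionality estimates in very small patient cohorts. Patient exposure is also what is compared with the healthy-subject limits (SAP 3.1.3).

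**Working it through.** **Dose counts**
- Parts D and E: Days 6 to 32 give 32 − 6 + 1 = 27 doses, matching the SAP's 27. Adding Day 1 gives 28.
- Extension: Days 1–2, 3–29, 30, 31–59, 60, 61–89 and 90 give 2 + 27 + 1 + 29 + 1 + 29 + 1 = 90, matching the SAP's 90.

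**Doses without a post-dose profile**
- Parts D and E: 28 − 3 = 25 (25/28 = 89%).
- Extension: 90 − 3 = 87 (87/90 = 97%).
- Vomiting on the day before a multiple-dose profile could lower the predose value. Setting those days aside (11 and 31; 29, 59 and 89) leaves 25 − 2 = 23 of 28 and 87 − 3 = 84 of 90.

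**Illustration of size**

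The documents give neither an emesis rate nor a median Tmax. Let p be an assumed probability, per dose, of vomiting within the window, independent between doses and equal for all subjects. The chance that a subject is excluded when m doses count is 1 − (1 − p)^m.

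| Assumed p | 3 profiled doses only | 28 doses | 90 doses |
|---|---|---|---|
| 0.5% | 1.5% | 13.1% | 36.3% |
| 1% | 3.0% | 24.5% | 59.5% |
| 2% | 5.9% | 43.2% | 83.8% |

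**Falling below the power-model minimum**

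A Part D or E cohort has 4 active subjects. Losing 2 leaves 4 − 2 = 2, below 3. With P the exclusion probability, the chance of losing at least 2 of 4 is 1 − (1 − P)^4 − 4P(1 − P)^3.

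| Assumed p | Subject-level rule, P from 28 doses | Profile-level rule, one profile day (P = p) |
|---|---|---|
| 0.5% | 8.6% | 0.02% |
| 1% | 25.4% | 0.06% |
| 2% | 57.9% | 0.23% |

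**Sensitivity to independence**

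Emesis may cluster in some subjects. A beta-binomial model with the same mean p and an assumed within-subject correlation of 0.1 gives, for p from 0.5% to 2%:
- exclusion over 28 doses: 6% to 23%
- exclusion over 90 doses: 10% to 36%
- at least 2 of 4 lost over 28 doses: 2% to 23%

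These are lower, but still well above the 1.3% to 5.3% that the same model gives for three profiled doses.

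**The case against.** **The reference dose is unstated, not expressly any dose.** A reader might infer that the SAP deliberately reaches every dose. It does not say so. SAP Table 6-2 defines Tmax only for Day 1 and the day of the last dose, so a window tied to a profiled dose is a possible reading. That stands. But it settles only the start of the window: the sentence would still remove the subject, so vomiting on Day 32 would still cost Days 1 and 12.

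**Other provisions soften the rule.** SAP 6.1.2 allows profile-level exclusion, with results shown with and without the excluded profiles. That is discretionary and does not modify a mandatory emesis sentence. Separate single- and multiple-dose populations (SAP 7.5) would protect Day 1 if adopted. They are optional, do not separate Day 12 from Day 32, and do not cover the Extension.

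**No data are destroyed.** Correct. The exclusion is from summaries and statistical analysis, and the values would still be listed.

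**The percentages have no source.** Correct. They rest on an assumed rate and on independence. Constant risk is also doubtful, because only subjects who tolerated the single dose go on to multiple dosing.

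**The 3-value minimum has limited reach.** It governs only the power model, which the protocol treats as optional (9.2.8); descriptive summaries continue. Table 6-2 plans no Day 12 parameters, so the loss there is to concentration summaries. In the Extension the minimum is moot if DE1 is the only cohort, since one dose level gives no slope. That part also has more active subjects (up to 12 in the SAP, up to 21 in the protocol).

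**Direction of bias.** It is tempting to infer that vomiting tracks high exposure, so that exclusion would understate exposure at poorly tolerated doses. The documents contain nothing that establishes this.

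**Conclusion.** Wrong as written: the rule is unsuited to the multiple-dose parts. Its stated unit (the subject) and scope (the study) would, if followed, remove valid profiles because of vomiting after an unprofiled dose or after a later profiled one. The missing reference dose adds a second ambiguity. No other provision in the SAP reliably cures either.

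The firm part of the size is structural: 25 of 28 doses and 87 of 90 carry no post-dose profile, and two exclusions among 4 active subjects breach the power-model minimum. The exclusion percentages are hypothetical. They show that the gap between the two rules is large across a plausible range, not what will happen in this trial.

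Two limits apply. Vomiting on the day before a profile may affect the predose sample, and longer carry-over depends on a half-life the documents do not give. Subjects may also enter more than one Part D or E cohort (Protocol 4.4), so a literal rule could reach profiles from another cohort; the calculation does not include this.

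**What to change.** Replace the emesis sentence in SAP 6.1.2 with:

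> If vomiting occurs at or before 2 times median Tmax after a dose with post-dose PK sampling, the profile for that dose (not the subject) is listed but excluded from PK summaries and statistical analysis; parameters that use that profile, such as Rac, are likewise excluded, and the subject's other profiles are retained. Emesis after other doses is listed; if it follows the dose on the day before a profile, the predose concentration is flagged and reviewed.

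This changes one rule in one section and needs no new data: SAP 3.1.4 already has home dose times on diary cards, and SAP 3.2.1 has adverse event start times. Profiles with vomiting on a PK day are still excluded, so any informative loss is reduced, not removed.

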6.1.3 Non-Quantifiable Concentrations

All concentration values reported as no results (not collected or not determined) values will be treated as missing. For the calculation of concentration summaries, all concentrations below the quantifiable limit (BLQ) will be treated as 0. For the purpose of calculating PK parameters and plotting mean and individual concentration-time profiles, concentrations below the lower limit of quantitation (BLQ) will be treated as zero prior to the the first quantifiable concentration; subsequent values BLQ concentrations will be treated as "missing."

7 STATISTICAL METHODS

7.1 General

The statistical analysis will be conducted following the principles specified in the International Council for Harmonization (ICH), formerly the International Conference of Harmonization, Topic E9 Statistical Principles for Clinical Trials (CPMP/ICH/363/96).

All statistical tabulations and analyses will be done using SAS®, Version 9.4 or higher.

Unless otherwise noted, for continuous outcomes, descriptive statistics will include the number of subjects, mean, 95% confidence interval (CI) for the mean, standard deviation (SD), median, minimum (Min), maximum (Max), 25th percentile, and 75th percentile. For categorical outcomes, the number and percentage of subjects will be presented. Descriptive statistics will generally be presented by AT-007 group. For summaries of continuous AT-007 PK concentration and parameter data, the coefficient of variation will also be presented.

In the data listings, study day relative to first dose of study drug may be presented. Study day relative to first dose will be calculated as: event date - first dose date (+ 1 if event day \geq first dose date).

For analyses of change from baseline, baseline will generally be defined as the predose assessment on Day 1 or Day -1, as scheduled. If this value is unavailable, the last non-missing value prior to dosing will be used.

All data from the CRFs, as well as any derived variables, will be presented in data listings.

For safety summaries, the unscheduled and repeat assessments will not be summarized; however, all results will be included in the data listing.

Unless otherwise noted, the analyses will be done by Parts and actual treatment/dose received.

Three sets of outputs will be created: One set for Part A, B, C, and D, one set for Part D Extension and one set for Part E(as detailed below). In creating tables in 3 sets, parts already completed can be analyzed earlier than the whole study has been completed.

| Study Part | Study Population | Design | Table |
|---------------------|---|---|---|
| Study 1 art | Study 1 opulation | Design | 1 abic |
| Part A | Healthy Adult Subjects | SAD | Parts A, B, C, and D will be |
| Part B | Healthy Adult Subjects | MAD (QD for 7 days) | summarized under 1 st set |
| Part C | Healthy Adult Subjects | MAD (QD for 7 days) | |
| Part D | Adult Subjects with CG | SAD, 5-day washout, MAD (QD for 27 days) | |
| Part D Extension | Adult Subjects with CG | MAD (QD for 90 Days) | Part D Extension will be summarized under 2 nd set |
| Part E | Adult Subjects with GALK- deficient Galactosemia | SAD, 5-day washout, MAD (QD for 27 days) | Part E will be summarized under 3 rd set |

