APPENDIX G. GUIDANCE IN CASE OF INCREASE IN ALT OR AST

1. If ALT or AST > 3x ULN and Total Bilirubin < 2x ULN:

- The event must be reported to the Sponsor within 24 hours.
- The following laboratory tests will be performed: alkaline phosphatase, total and conjugated bilirubin, prothrombin time, international normalized ratio (INR), creatinine phosphokinase (CPK), serum creatinine, complete blood count, hepatitis A virus (HAV), hepatitis B virus (HBV), hepatitis C virus (HCV), hepatitis D virus (HDV), and hepatitis E virus (HEV).
- Recent medical history will be investigated specifically for intercurrent illness, malaise with or without loss of consciousness, dizziness, hypotension, episodes of arrhythmia, and muscular injury.
- Concomitant medications, including recreational drugs, nonprescription medications and herbal and dietary supplement preparations, will be reviewed and any substance potentially responsible for the elevation of liver enzymes will be discontinued, if possible
- Information on potential exposure to environmental chemical agents, alcohol use, and special diets, including adherence to a galactose-restricted diet, will be collected and any factor potentially responsible for the elevation of liver enzymes will be addressed, if possible
- If the patient is asymptomatic and the ALT/AST elevation is not associated with abnormal liver function (e.g. increased bilirubin or abnormal coagulation parameters), the STUDY TREATMENT WILL BE CONTINUED UNDER STRICT MONITORING as below.
- Liver function tests (LFTs) will be monitored every two weeks x2 and then monthly for six months. If ALT or AST decrease to below 3x ULN, then monthly monitoring will continue until resolution. If ALT or AST increase to >5x ULN or if Total Bilirubin increases to >2x ULN, implement the below procedures.
- For ALT or AST >3x ULN lasting six months, perform a hepatic ultrasound and consult with a hepatologist

2. If ALT or AST > 5x ULN OR if ALT or AST >3x ULN and Total Bilirbuin >2x ULN, a retest must be performed within 24 hours

2a. If confirmed ALT or AST > 5x ULN OR if ALT or AST >3x ULN and Total Bilirbuin >2x ULN:

- The event must be reported to the Sponsor within 24 hours.
- STUDY TREATMENT WILL BE DISCONTINUED.
- The following laboratory tests will be performed: alkaline phosphatase, total and conjugated bilirubin, prothrombin time, international normalized ratio (INR), CPK,

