serum creatinine, complete blood count, hepatitis A virus (HAV), hepatitis B virus (HBV), hepatitis C virus (HCV), hepatitis D virus (HDV) and hepatitis E virus (HEV)

- A 2 mL serum sample will be collected and stored frozen for future analysis
- An hepatobiliary ultrasonography will be performed.
- All necessary investigations will be performed to rule out autoimmune or alcoholic hepatitis; non-alcoholic steatohepatitis (NASH); biliary tract disease, and hypoxic/ischemic hepatopathy (possibly due to right heart failure or other cardiovascular disease)
- Recent medical history will be investigated specifically for malaise with or without loss of consciousness, dizziness, hypotension, episodes of arrhythmia, and muscular injury.
- Concomitant medications, including recreational drugs, nonprescription medications and herbal and dietary supplement preparations, will be reviewed
- Information on potential exposure to environmental chemical agents, alcohol use, and special diets, including adherence to a galactose-restricted diet, will be collected
- A consult with an hepatologist will be requested.
- Liver Function tests (LFTs) will continue to be monitored every 48 hours until stabilization and symptoms remission (if any), then every 2 weeks until normalization.

2b. If ALT or AST $> 5x$ ULN OR if ALT or AST $> 3x$ ULN and Total Bilirbuin $> 2x$ ULN not confirmed and ALT or AST is $< 5x$ ULN and $> 3x$ ULN (with Total Bilirbuin $< 2x$ ULN) all the procedures listed above under section 1 will be implemented.

2c. ALT or AST $< 3x$ ULN but $> 1.5x$ ULN:

- The event must be reported to the Sponsor within 24 hours.
- LFTs will continue to be monitored every month until normalization or further elevation. If ALT or AST $> 3 x$ ULN, all the procedure above in section 1 will be implemented. If ALT/AST $> 5x$ ULN, OR if ALT or AST $> 3x$ ULN and Total Bilirbuin $> 2x$ ULN, all the procedures listed above under section 2 will be implemented.

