APPENDIX H. GUIDANCE IN CASE OF WORSENING RENAL FUNCTION

Renal function must be closely monitored during the study, particularly during administration of potentially nephrotoxic drugs, such as acetaminophen, non-steroidal anti-inflammatory drugs (NSAIDs), fluoxetine, antihistamines, antimicrobials, benzodiazepines, proton pump inhibitors, phenytoin, trimethoprim, fenofibrate, cimetidine, cephalosporins, probenecid, aminoglycoside, amphotericin, ketoconazole, and clofibrate

Urine protein-to-creatinine ratio (UPCR), urine albumin-to- creatinine ratio (UACR) and eGFR will be assessed at each visit. In case of increased UPCR (≥ 200 mg/g), increased UACR (≥ 30 mg/g), eGFR < 30 mL/min/1.73 m², or decreased eGFR $> 30\%$ compared to baseline, a retest must be performed within 24 hours and if the abnormal laboratory result is confirmed, the following actions will be taken:

- The event must be reported to the Sponsor within 24 hours
- Concomitant medications will be reviewed and any potentially nephrotoxic drug must be discontinued
- Recent medical history will be investigated specifically for significant increase or decrease of blood pressure, plasma volume depletion, flu-like symptoms, urinary tract infection, and abdominal pain suggestive of obstructive uropathy.
- If there is no suspected concomitant medication , or if no improvement of renal function is observed after 72 hours of discontinuation of the potentially nephrotoxic drug, and if there is nothing in recent medical history that is likely to cause the abnormal renal function, the study drug will be temporarily discontinued.
- The following urinary markers of kidney injury must be measured: Clusterin (CLU), Cystatin-C (CysC), Kidney Injury Molecule-1 (KIM-1), N-acetyl-beta-D-glucosaminidase (NAG), Neutrophil gelatinase-associated lipocalin (NGAL), and Osteopontin (OPN)
- A renal ultrasound will be performed.
- A nephrologist will be consulted
- Renal function (eGFR, UPCR and UACR) will continue to be monitored every 48 hours until stabilization, then every 2 weeks until normalization.
- At this time, the Investigator in consultation with the nephrologist will decide if the study drug may resume

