7.12.3 Clinical Laboratory Assessments

Observed and change from baseline of continuous clinical laboratory values (serum chemistry, hematology, coagulation, and urinalysis) for each parameter will be summarized by Part and cohort at each scheduled nominal time point. The number and percentage of subjects with shift changes from baseline based on the laboratory normal ranges will be tabulated. Laboratory data will be listed by subject at each time point. Clinical laboratory values that are out of normal ranges will be presented in a separate listing. Urinalysis laboratory tests will be presented in data listings only.

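### Laboratory summary tables omit the confirmatory retests and between-visit peaks that Appendices G and H generate, and no planned table counts subjects who met those thresholds

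*SAP*

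**What the plan says.** SAP 7.1 sets the general rule: "For safety summaries, the unscheduled and repeat assessments will not be summarized; however, all results will be included in the data listing". For laboratory data, SAP 7.12.3 says that observed values and changes from baseline "will be summarized by Part and cohort at each scheduled nominal time point". It adds: "The number and percentage of subjects with shift changes from baseline based on the laboratory normal ranges will be tabulated". It also says: "Clinical laboratory values that are out of normal ranges will be presented in a separate listing". The matching outputs in SAP 8 are the abnormal-value listing (14.3.4.1 series), the by-visit summary (14.3.4.2), the shift table (14.3.4.3) and the full laboratory listing (16.2.8.2). None is built on a worst post-baseline value. None counts subjects by multiple of the ULN, by confirmed elevation or by change in a renal marker.

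Protocol 3.5 points to Appendices G and H for the criteria that stop dosing in an individual subject. For ALT or AST above 5x ULN, or above 3x ULN with total bilirubin above 2x ULN, Appendix G says that "a retest must be performed within 24 hours". Action on study treatment follows the confirmed result, with liver tests then every 48 hours and later every 2 weeks. Its lower tier (section 1) calls for two tests at two-week intervals and then monthly tests. Appendix H also requires a retest within 24 hours when UPCR, UACR or eGFR crosses its limits, after which renal function "will continue to be monitored every 48 hours until stabilization, then every 2 weeks until normalization".

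**The concern.** Safety is the primary objective, and hepatic and renal function are the two areas for which the protocol sets numeric on-treatment laboratory thresholds. The decisive result under each appendix is the retest, and the highest value may come during follow-up. If neither can enter a summary table, the laboratory summaries can mislead in two directions:

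- A rise that grows after a scheduled visit is shown at its earlier, lower level.
- A scheduled spike that the retest does not confirm (Appendix G, 2b) stays in the table, while the value that refuted it is left out.

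The shift tables do not repair this. They use normal ranges, so a value just above the ULN and one several times the ULN fall in the same category. A reader of the study report could not tell from the laboratory tables how many subjects on each dose, or on placebo, met a stopping threshold and had it confirmed.

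**Working it through.** The plan gives no figure to reproduce. The check is whether the tests that Appendices G and H require can fall on a draw that the SAP summarizes.

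**Inputs.** Scheduled post-dose laboratory days come from SAP 3.2.2. The EOS and EOE days (28, 35, 60 and 118) come from Protocol 6.9. Visit windows come from Protocol Appendix D note q, Appendix E note o and Appendix F note a.

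**Gap between consecutive scheduled draws (later day minus earlier day).**

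| Part | Post-dose laboratory days | Gaps (days) |
|---|---|---|
| A | 3, 28 | 25 |
| B and C | 6, 35 | 29 |
| D and E | 6, 12, 20, 32, 60 | 6, 8, 12, 28 |
| D Extension | 30, 60, 90, 118 | 30, 30, 28 |

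The shortest gap is 12 − 6 = 6 days. If the Day 6 visit is one day late and the Day 12 visit one day early, it is 6 − 1 − 1 = 4 days.

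**24-hour retest.** One day is less than 4, so a retest of a scheduled post-dose value is never itself a scheduled draw. SAP 7.1 excludes it from summaries in every part.

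**48-hourly follow-up.** The protocol gives no fixed duration. As an illustrative upper case, suppose that it lasts for a whole gap. The draws strictly between two scheduled ones then number (gap − 1)/2, rounded down:

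- Parts D and E: 2, 3, 5 and 13.
- Part D Extension: 14, 14 and 13.

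Put another way, 14 days of 48-hourly testing gives 14/2 = 7 results and 28 days gives 28/2 = 14. The last of those 14 could coincide with a scheduled visit if the gap is exactly 28 days.

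**Two-weekly and monthly tests.** Take a lower-tier elevation at Extension Day 30. The tests fall at about Days 30 + 14 = 44, 44 + 14 = 58 and 58 + 30 = 88. Extension visits after Day 2 have a window of ±2 days, so Day 58 fits the Day 60 visit and the monthly test can coincide with the Day 90 visit. Day 44 is off schedule. Some of these tests are therefore summarized and some are not.

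**Illustration (values invented).** If ALT is 4x ULN at Day 30 and 7x ULN at Day 44, the scheduled tables carry the 4x value for this subject. The 7x value and its retest appear only in listings.

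**Renal markers.** SAP 3.2.2 does not name UACR, UPCR or eGFR among the laboratory tests. SAP 7.12.3 first includes urinalysis among the summarized values and then restricts it to listings. So even scheduled values of these markers have no specified summary, whatever SAP 7.1 says. Collection is also unclear. Appendix H assesses the markers at each visit. The Part A schedule and the Extension laboratory footnote name UACR and UPCR, but the laboratory rows and footnotes for Parts B to E do not name them at on-treatment visits.

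**The case against.** Much can be said for the plan. Keeping unscheduled values out of by-visit means is sound, because otherwise retested subjects would be over-represented. Nothing is lost from the record: all results are listed, and out-of-range values have their own Section 14 listing by subject. The by-visit summaries report the maximum, so a high scheduled value remains visible. An abnormal laboratory finding can be an AE (Protocol 8.1.1), and the TEAE tables count events by severity, relationship and whether they led to discontinuation. Most cohorts have 4 to 6 subjects on AT-007, with up to 21 in the Extension, so a listing can be read directly.

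These points limit the concern but do not remove it. A listing gives no counts by dose and placebo. The AE route is not automatic: Protocol 7.1.3 and 7.1.4 require clinically significant examination and vital-sign findings to be reported as AEs, but 7.1.2 has no such statement for laboratory values. The TEAE tables also do not show ULN multiples or retest confirmation, and the temporary interruption under Appendix H need not count as a discontinuation.

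A reader might infer more than the documents support:

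- **That the hepatic and renal rules run only on off-schedule tests.** The triggering value can be a scheduled one, and some follow-up tests can fall within a visit window.
- **That these results vanish from every summary.** The loss is confined to the laboratory summary tables.
- **That Appendices G and H are the only numeric safety rules.** Protocol 3.5 also stops escalation at two or more subjects with a DLT.
- **That SAP 7.1 makes later visit means look better when a subject stops.** Any such effect would come from discontinuation and the absence of imputation (SAP 7.2).
- **That SAP 7.1 alone causes the renal gap.** The markers are absent from the SAP laboratory list.

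**Conclusion.** The point holds as a reporting gap in the primary safety analysis. Applied as written, the SAP leaves out of the laboratory summary tables every 24-hour retest of a scheduled post-dose value, most 48-hourly follow-up and some two-weekly follow-up. No worst-value or threshold table recovers them. The retest result follows directly from the schedule and needs no assumption beyond visits being held within their windows.

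How many follow-up values are lost in practice cannot be stated, because it depends on how many subjects trigger a rule and how long they take to stabilize. The counts of 7 and 14 tests and the 4x-to-7x case are illustrations only. For renal markers the larger cause is their omission from the SAP. The SAP cites protocol Version 6.0 and an Extension of 16 subjects, against 28 in the protocol supplied, so it may not have been aligned with the current appendices. The documents do not say when those were added.

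**What to change.** 1. Keep the by-visit tables on scheduled values.
2. In SAP 7.1 and 7.12.3, derive each subject's worst post-baseline value from all scheduled, unscheduled and repeat results, and use it for the shift tables.
3. Add one table per part counting subjects, by AT-007 dose and placebo, who met each Appendix G hepatic threshold, with initial and retest-confirmed counts side by side.
4. Add UACR, UPCR and eGFR to the laboratory list in SAP 3.2.2, resolve the two statements on urinalysis in 7.12.3, and give the same counts for the Appendix H thresholds where the data were collected.
5. Reconcile the Part B to E schedules with the statement in Appendix H that the renal markers are assessed at each visit.

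For liver tests the cost is SAP wording and one or two tables per part, with no new data. For renal markers, what can be tabulated depends on what each part collected. One small drawback is that retested subjects contribute more observations, so their worst values run slightly higher. Showing initial and confirmed counts together makes that visible.
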